2.5. Efficacy and Safety Variables

2.5.1. Efficacy Variables

Primary endpoint:

- Emergency room visit due to the clinical worsening of COVID-19 (defined as participants remaining under observation for > 6 hours) within 28 days of randomization
- Hospitalization due to the progression of COVID-19 (defined as worsening of viral pneumonia) and/or complications within 28 days of randomization

Secondary endpoints:

- Viral clearance and viral load on D3 and D7 after randomization;
- Time (in days) to clinical improvement (up to 28 days of randomization), defined as the first day on which the participants report a score of 0 on the World Health Organization (WHO) Clinical Worsening Scale;
- Time (in days) to clinical failure;
- Number of days with respiratory symptoms since randomization;
- Hospitalization for any causes;
- Time to hospitalization due to COVID-19 progression;
- Mortality due to pulmonary complications;
- Mortality due to cardiovascular complications;
- Mortality from any causes;
- Adverse events that occurred (up to 28 days);
- Adverse drug reactions;
- WHO clinical worsening scale over the follow-up period;
- WHO clinical worsening scale during the treatment phase;
- PROMIS global health scale scores (days 14 and 28).

Statistical Analysis Plan

Sponsor:	McMaster University		
Protocol:	TOGETHER trial		
Document Version No.:	1.1	Document Date:	05-May-2021

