4. STATISTICAL METHODS

4.1. Sample Size Justification

The sample size of 681 patients per arm has been chosen for each experimental group to achieve 80% power with 0.05 two-sided Type 1 error for a pairwise comparison against the control to detect minimum treatment efficacy defined by 37.5% relative risk reduction (RRR) of preventing hospitalization assuming a control event rate (CER) of 15%.

Statistical Analysis Plan

Sponsor:	McMaster University		
Protocol:	TOGETHER trial		
Document Version No.:	1.1	Document Date:	05-May-2021

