4.2. General Statistical Methods and Data Handling

4.2.1. General Methods

All output will be incorporated into Microsoft Excel or Word files, sorted and labeled according to the International Conference on Harmonisation (ICH) recommendations, and formatted to the appropriate page size(s).

Tabulations will be produced for appropriate demographic, baseline, efficacy, and safety parameters. For categorical variables, summary tabulations of the number and percentage within each category (with a category for missing data) of the parameter will be presented. For continuous variables, the mean, median, standard deviation, minimum and maximum values will be presented. Time to event data will be summarized using Bayesian Kaplan-Meier estimates.

Bayesian bivariate analysis will be performed on secondary efficacy endpoints outlined in 2.5.1. Summary statistics will be presented, as well as their corresponding 95% credible intervals.

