4.2.3. Statistical Analysis Details

4.2.3.1. Bayesian inference for dichotomous outcomes with covariate adjustment

Here we may use the generalized linear model framework for binary outcome with the logistic link function, namely

$$y_i \sim \text{Binom}(1, p_i)$$

with

$$\log \frac{p_i}{1 - p_i} = x_i^T \beta + \gamma T_i,$$

using the same notations as before. Assigning a noninformative prior distribution $p(\beta, \gamma) \propto 1$, the logarithm of the posterior distribution (after some simple algebra) is given by

$$\begin{aligned} \log p(\beta, \gamma | \mathbf{y}) &= \log p(\beta, \gamma) + \sum_{i=1}^n \log p(y_i | \beta, \gamma) \\ &= \sum_{i=1}^n \{y_i(x_i^T \beta + \gamma T_i) - \log[1 + \exp(x_i^T \beta + \gamma T_i)]\}, \quad (1) \end{aligned}$$

and a random sample from $p(\beta, \gamma | \mathbf{y})$ may then be drawn using Markov Chain Monte Carlo (MCMC) such as the Metropolis-Hastings algorithm¹ using (5) or Gibbs sampling using any software for Hierarchical Bayesian modeling such as BUGS² or JAGS³. Inference on the treatment effect will then follow the same procedure as in the numeric case.

The treatment effects on dichotomous outcomes will be estimated using R.

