4.6. Efficacy Evaluation

Efficacy analysis will be conducted using the ITT and PP Populations as outlined below. The two primary endpoints will be analyzed as a composite. Secondary endpoints will be assessed within 28 days of randomization, unless stated differently.

Table 3: Objectives and Endpoints

Objectives	Endpoints
Primary	

 Reduction in the need for emergency room visits due to the clinical worsening of COVID-19 and keeping the participant under observation for > 6 hours within 28 days of randomization in acutely affected patients and with evidence of high-risk for complications 	
 Proportion of those in need of emergency care under observation for more than 6 hours for COVID-19

 Reduction in the need for hospitalization due to the progression of COVID-19 (worsening of viral pneumonia) or complications within 28 days of randomization in acutely affected patients and with evidence of high-risk for complications 	
 Proportion of those in need of hospitalization due to progression of COVID-19 and/or complications
Secondary	

 To test the efficacy of experimental interventions to reduce SARS-CoV-2 viral shedding at day 3 and day 7 	
 Proportion of persons with clearance of SARS-CoV-2 from nasal swabs or saliva, defined as 1 negative swab Proportion of days with SARS-CoV-2 detected from mid-nasal swabs by PCR Change in viral load on day 3 and day 7 compared to baseline

 To test whether any of the experimental interventions decrease time to resolution for symptomatic SARS-CoV-2 infection / COVID-19 disease 	
 Time to clinical improvement (up to 28 days of randomization), defined as the first day on which the participant reports a score of 0 on the WHO Clinical Worsening Scale

Statistical Analysis Plan

Sponsor:	McMaster University		
Protocol:	TOGETHER trial		
Document Version No.:	1.1	Document Date:	05-May-2021

	
 • Time to clinical failure • Number of days with respiratory symptoms after randomization • Proportion of patients on each scale of the WHO clinical worsening scale over the treatment period and over the follow-up period

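### The ordinal WHO Clinical Worsening Scale is summarised only as proportions at each level, and the SAP names no model that uses the ordering or gives one treatment effect

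*SAP*

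**What the plan says.** SAP section 2.5.1 lists the scale twice among the secondary endpoints, once for the treatment phase and once as "WHO clinical worsening scale over the follow-up period", with no summary measure. The schedule of activities in section 2.4 records it at screening and at every contact from Day 1 to Day 60.

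The only summary measure is in section 4.6, Table 3: "Proportion of patients on each scale of the WHO clinical worsening scale over the treatment period and over the follow-up period". It stands under an objective framed as a test of whether treatment shortens time to resolution.

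On method, section 4.2.1 says "Bayesian bivariate analysis will be performed on secondary efficacy endpoints outlined in 2.5.1" and promises 95% credible intervals. Section 4.2.3 writes out two models. One is a "generalized linear model framework for binary outcome with the logistic link function"; the other is a piecewise-constant proportional hazards model. Neither is ordinal.

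The scale is used once more, for time to clinical improvement, defined as the "first day on which the participants report a score of 0 on the World Health Organization (WHO) Clinical Worsening Scale".

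**The concern.** An ordinal scale carries its information in the order of its levels. A list of proportions, one per level, does not use that order, which has three consequences.

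- **Direction.** Fewer patients at a middle level can mean that they got better or that they got worse. That row cannot be read as benefit or harm on its own.
- **No single answer.** Each period yields as many contrasts as there are levels. Section 4.2.4 covers subgroups, arms and repeated looks, but not several levels of one endpoint. A reader can pick the level that shows something.
- **Undefined period.** The score is repeated, and the SAP does not say which assessments make up each period. Section 4.6 limits secondary endpoints to 28 days unless stated otherwise, while section 4.2.8 runs the post-treatment interval to Day 60.

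At stake is the usefulness of one secondary endpoint that could show an effect on milder illness as well as on hospitalisation.

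**Working it through.** The SAP gives no power for this endpoint, so there is no stated figure to reproduce. The calculation below shows what an ordered analysis could be worth, and when it is worth nothing.

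**Inputs from the SAP.** 681 per arm and two-sided 0.05 (section 4.1); control event rate 15% (section 4.1); the RRR 20% scenario (section 4.3). The last two belong to the binary primary endpoint.

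**Assumptions not in the SAP.** Six levels, 0 to 5. Controls have 15% in the top three levels (split 8%, 5%, 2%), score 0 in 30%, 50%, 70% or 82%, and the remainder split equally between levels 1 and 2. One cross-sectional comparison, with the same odds ratio at every cut.

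**Odds ratio.** (0.12/0.88) / (0.15/0.85) = 0.1364/0.1765 = 0.773; its log is -0.258.

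**Ordinal power, 30% scenario.** The odds ratio moves score 0 from 30.0% to 35.7%, level 1 from 27.5% to 28.0% and level 2 from 27.5% to 24.4%. Whitehead's information is V = n² × 2n / [3(2n+1)²] × (1 - Σp̄³), where p̄ is the mean of the two arms at each level. The first factor is 113.3 and the second 0.925, so V = 104.9. Power = Φ(√104.9 × 0.258 - 1.96) = Φ(0.68) = 75%.

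**Single cut at score 0, same scenario.** z = (0.3568 - 0.3000) / √(2 × 0.3284 × 0.6716 / 681) = 2.23. Power = Φ(2.23 - 1.96) = 61%.

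**Level-wise tests, same scenario.** At 0.05/6 the critical value is 2.64. Expected z values for levels 0 to 5 are 2.23, 0.19, -1.33, -1.06, -0.94 and -0.63. Simulated power to reject at one or more levels is 44%.

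**All four scenarios** (simulation, 40,000 runs each):

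| Controls at score 0 | Ordinal | Level-wise, 0.05/6 | Gain | Cut at score 0 | Gain |
|---|---|---|---|---|---|
| 30% | 75% | 44% | 31 | 61% | 14 |
| 50% | 71% | 46% | 25 | 65% | 6 |
| 70% | 58% | 37% | 21 | 56% | 1 |
| 82% | 42% | 25% | 17 | 42% | 0 |

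At RRR 37.5% (odds ratio 0.586) the gap narrows, because both are high: 94% to 100% against 82% to 99%.

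**No true effect.** At least one of six unadjusted level-wise tests at 0.05 rejects in 24% to 25% of runs; the ordinal test rejects in about 5%.

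**Direction of a middle level.** Under the same beneficial odds ratio, level 1 rises from 27.5% to 28.0% in the 30% scenario and falls from 17.5% to 16.5% in the 50% scenario.

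**Other comparator and other numbers of levels.** Against an unordered chi-square test, over 1,365 randomly drawn distributions with three to eight levels, the ordinal gain runs from 8 to 31 points. The median is 10 points for three levels, 25 for six and 31 for eight.

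**Without proportional odds.** Suppose the top three levels each fall by a fifth (15% to 12% in total), those patients move only to the adjacent level, and milder levels do not change. In the four scenarios above, the ordinal test then has about 6% to 7% power and the level-wise tests about 20% to 77%. In a further case with the other 85% all at one level, the ordinal test still leads an unordered test, 37% to 20%.

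**The case against.** A reader might infer that the SAP commits to testing the scale level by level and so forfeits 17 to 31 points of power. The documents do not support that. Table 3 lists objectives and endpoints; it names no test. The binary model itself is introduced permissively ("Here we may use the generalized linear model framework for binary outcome with the logistic link function"). The written models are also not exhaustive: section 4.2.3.1 refers to a numeric case that is not written out, and viral load and PROMIS change have no model either. The level proportions may be meant as description. The SAP never mentions six tests with a Bonferroni correction, so the plan has no such power to lose.

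The inputs are open to the same objection. The number of levels and their distribution are assumed. The 15% and the RRR 20% describe a 28-day composite that includes emergency room observation, which the SAP does not map to any level of the scale. Time to a first score of 0 already uses the main contrast, which is why the gain over a single cut is only 0 to 14 points. The benefit also depends on roughly proportional odds.

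All of this stands, and it turns the figures into illustrations. It does not remove the gap. The endpoint sits under an objective to be tested, intervals are promised for it, its only stated summary ignores order, and no passage supplies a single ordered effect.

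**Conclusion.** The concern holds in limited form. The SAP states one summary for this ordinal endpoint, the proportion at each level over two periods, and names no analysis that uses the ordering. With the models it does write out, the result would be several contrasts, some without direction, and no overall effect.

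The size is conditional. With six assumed levels, 681 per arm and a common odds ratio of 0.77 carried over from the primary endpoint, an ordinal analysis gains about 17 to 31 points over Bonferroni level-wise tests and 0 to 14 over a cut at score 0. Unadjusted level-wise reading gives about a 25% chance of at least one false difference per comparison of the arms. The ordering can reverse if benefit is confined to the hospitalised levels. The figures describe one cross-sectional comparison, not a repeated-measures model.

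This is a cheap improvement to a secondary endpoint. It does not touch the primary conclusion or the stopping rules.

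**What to change.** In section 4.6, Table 3, and with a matching model in section 4.2.3:

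- Make the inferential summary one common odds ratio with its 95% credible interval for each period, from a Bayesian cumulative-logit model on the full scale, with death as the worst level.
- Adjust for the screening score and for the age and symptom-onset strata.
- State which scheduled assessments within 28 days define the treatment period and which define the follow-up period. Handle repeated scores with a patient random effect.
- State the number of levels.
- Keep the level proportions as a descriptive table, and name that table as the check on proportional odds.

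The cost is SAP wording and one standard model; the data are already collected. The downside is that the common odds ratio relies on approximately proportional odds and can miss an effect confined to the severe levels, so the level table must be reported beside it.

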4.7. Safety Analyses

Safety analyses will be conducted using the Safety Population.

4.7.1. Adverse Events

Adverse events will be coded using the Medical Dictionary for Regulatory Activities (MedDRA) and displayed in tables and listings using System/Organ/Class (SOC) and Preferred Term.

Statistical Analysis Plan

Sponsor:	McMaster University		
Protocol:	TOGETHER trial		
Document Version No.:	1.1	Document Date:	05-May-2021

Analyses of adverse events will be performed for those events that are considered treatment emergent, where treatment emergent is defined as any adverse event with onset after the administration of study medication or any event that was present at baseline but worsened in intensity or was subsequently considered drug-related by the investigator through the end of the study.

Adverse events are summarized by subject incidence rates, therefore, in any tabulation, a subject contributes only once to the count for a given adverse event (SOC or preferred term).

The number and percentage of subjects with any treatment-emergent adverse events assessed by the Investigator as related to treatment (definite, probable, or possible relationship), and with any serious adverse event will be summarized by treatment group and overall. In these tabulations, each subject will contribute only once (i.e., the most related occurrence or the most intense occurrence) to each of the incidence rates in the descriptive analysis, regardless of the number of episodes.

No formal hypothesis-testing analysis of adverse events incidence rates will be performed.

All adverse events occurring on study will be listed in subject data listings.

By-subject listings also will be provided for the following: subject deaths; serious adverse events; and adverse events leading to withdrawal.

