2.2. Randomization Methodology

Eligible participants will be randomized at an equal allocation ratio to study experimental intervention(s) or placebo. Individual randomization will be stratified by clinical site, by age (<50 years vs. ≥50 years), and time from onset of symptoms (<120 hours vs. ≥120 hours). The randomization sequence for each clinical site will be prepared by the unblinded statistician and will be sent to the unblinded pharmacist at each participating clinical site. Allocation of treatment assignment will be concealed from all other study personnel.

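### If COVID-19 hospitalisations are recorded as serious adverse events, the single pooled by-arm count of serious events in SAP 4.7.1 largely restates the efficacy result

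*SAP*

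**What the plan says.** SAP 4.7.1 (Adverse Events) gives the number and percentage of subjects with investigator-related treatment-emergent events and those "with any serious adverse event will be summarized by treatment group and overall". This is the only by-arm count of serious events in the plan. Each subject counts once.

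In the same section, "treatment emergent is defined as any adverse event with onset after the administration of study medication", and the definition also takes in conditions present at baseline that later worsen. Neither limb sets COVID-19 progression apart.

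SAP 2.5.1 names as one part of the primary endpoint: "Hospitalization due to the progression of COVID-19 (defined as worsening of viral pneumonia) and/or complications within 28 days of randomization". The other part is an emergency room stay of more than 6 hours for clinical worsening. SAP 4.6 analyses the two as a composite.

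SAP 4.1 sets the design values: "The sample size of 681 patients per arm has been chosen for each experimental group", with the effect expressed as "37.5% relative risk reduction (RRR) of preventing hospitalization assuming a control event rate (CER) of 15"%.

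SAP 4.7.1 also plans displays by System Organ Class and Preferred Term, and by-subject listings of deaths, serious events and events leading to withdrawal. It rules out formal testing of event rates. The SAP does not define what makes an event serious, and does not say whether endpoint events are exempt from adverse event reporting.

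**The concern.** Every patient enters with COVID-19. A later admission for worsening pneumonia begins after dosing and is a worsening of a condition present at baseline, so it fits the treatment-emergent wording if it is reported as an adverse event at all. An admission would then be counted twice: as a primary efficacy event and in the serious-event row.

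In that case the row adds together two things that a reader needs apart: admissions that the drug prevents, and serious events that it causes. A drug that works lowers the first count, and this can offset a rise in the second. The row could look balanced, or favour the drug, while other serious events are more frequent on it. Because no formal testing is planned, readers rely on the rows being interpretable as they stand.

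**Working it through.** **The plan's own figures.** The SAP gives no expected serious-event rate, so there is no stated figure on this point to reproduce. The arm size of 681 is used only as stated. For the record, the usual two-proportion formula with the inputs of SAP 4.1 (15% against 9.375%, two-sided 0.05, 80% power) gives 530 per arm, not 681. That is a separate matter and does not affect the check below.

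**Inputs.**
- Control rate p_c = 0.15, relative risk reduction 37.5%, n = 681 per arm (SAP 4.1); equal allocation (SAP 2.2).
- Active rate p_a = 0.15 × (1 − 0.375) = 0.09375.
- Assumed: each endpoint event is recorded as serious; other serious events have a background rate s of 0% to 5% (the SAP gives none); the two kinds of event are independent.

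**Step 1: patients entering through the endpoint alone.**
- Control: 0.15 × 681 = 102.2
- Active: 0.09375 × 681 = 63.8
- Gap: 38.3 patients, or 5.6 points

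**Step 2: how much of the row is the endpoint.** With one count per subject, the pooled control rate is 1 − (1 − p_c)(1 − s).
- s = 2%: 1 − 0.85 × 0.98 = 16.7%, and 15.0 / 16.7 = 90% of these patients have an endpoint event.
- s = 5%: 1 − 0.85 × 0.95 = 19.25%, and 15.0 / 19.25 = 78%.

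**Step 3: the drug-caused excess e that balances the row.** Setting (1 − p_a)(1 − s − e) = (1 − p_c)(1 − s) gives

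e = (1 − s) × (p_c − p_a) / (1 − p_a) = (1 − s) × 0.05625 / 0.90625 = (1 − s) × 0.0621.

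- s = 0%: 6.2 points
- s = 2%: 6.1 points
- s = 5%: 5.9 points

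This is slightly more than the 5.6-point gap, because a drug-caused event in a patient already counted adds nothing to the row.

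**Step 4: an example.** Background 2%, doubled to 4% by the drug:

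| Row | Control | Active |
|---|---|---|
| All serious events | 1 − 0.85 × 0.98 = 16.7% | 1 − 0.90625 × 0.96 = 13.0% |
| Without endpoint events | 2.0% (about 14 patients) | 4.0% (about 27 patients) |

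The first row favours the drug; the second shows the doubling.

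**Step 5: smaller effects.**
- Reduction of 20%: the endpoint gap is 0.15 × 0.20 = 3.0 points, about 20 patients.
- Reduction of 0%: the gap is zero and nothing is offset.

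**Step 6: if only part of the 15% is serious.** SAP 4.1 words the 15% as hospitalisation, but the primary composite also has emergency stays over 6 hours. If, say, half of the events were serious and the relative reduction were the same, the gap would halve to 0.5 × 5.6 = 2.8 points, about 19 patients.

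**The case against.** **The premise is not in the document.** A reader might infer that the table does count efficacy events as serious adverse events. The SAP does not say so. Its treatment-emergent definition applies only to what is already an adverse event, and both the definition of serious and any exemption for endpoint events are commonly left to the protocol. This stands, and the point has to remain conditional. What belongs to the SAP is the tabulation rule, which as written has no provision for the case in which endpoint events are reported.

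**Other outputs are planned.** A reader might also infer that the safety analysis as a whole could conceal harm. That does not follow. System Organ Class and Preferred Term tables would show a cardiac or hepatic term apart from COVID-19 pneumonia. Related events are tabulated by arm, and every serious event is listed. All-cause and COVID-19 hospitalisation are both efficacy endpoints, and their difference indicates the non-COVID part. This largely stands and confines the problem to the pooled row. These outputs do not fully replace the missing row, however. The term tables and the related-event summary are not said to be split by seriousness, the latter depends on causality judgement, and listings are not by-arm counts.

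**Excluding events has its own risk.** It is tempting to make the table without endpoint events the basis of the safety conclusion. If the drug worsens the disease, or its cardiac or pulmonary harm is attributed to COVID-19, that harm would drop out of such a table. Counting all serious events whatever their attribution is a defensible choice. This stands: neither table should be decisive.

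**Conclusion.** The point holds in conditional form and is minor. The SAP makes no false statement and contains no contradiction here; it leaves one descriptive row open to misreading. The size, an offset of about 6 points at the full design effect, rests on three assumptions: COVID-19 hospitalisations are recorded as serious, the 15% is close to the rate of serious endpoint events, and other serious events occur independently at 0% to 5%. The offset shrinks with a smaller treatment effect or a smaller serious share of the composite. It disappears if the drug has no effect on the endpoint or if the protocol exempts endpoint events from reporting.

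**What to change.** In SAP 4.7.1:
- State whether COVID-19 progression events enter the serious-event count.
- Keep the table of all serious adverse events by arm.
- Add a by-arm table of serious adverse events that leaves out those meeting a primary-endpoint component or recorded as COVID-19 progression, using the classification already made for the efficacy analysis.
- Say that the two tables are read together and that neither decides the safety conclusion alone.

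The cost is a few lines of wording and one more table from data already collected. If the protocol exempts endpoint events, the added table does no harm. The downside is that it depends on attribution to COVID-19: drug harm wrongly attributed to the disease would show only in the all-events table, which is why that table stays.
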